## 8.2. Exclusion Criteria

Subjects meeting **any** of the following criteria must be excluded from the study:

1. Any significant medical condition, laboratory abnormality, or psychiatric illness that would prevent the subject from participating in the study, including the presence of laboratory abnormalities that may place the subject at unacceptable risk if he/she were to participate in the study.

2. Any situation or condition that confounds the ability to interpret data from the study (e.g., subjects also receiving RBC transfusions at centers not able to obtain laboratory samples for central processing).
3. Diagnosis of  $\alpha$ -thalassemia (e.g., HbH) or HbS/ $\beta$ -thalassemia.
4. Body mass index (BMI)  $<17.0 \text{ kg/m}^2$  or a total body weight  $<45 \text{ kg}$ ; or BMI  $>35 \text{ kg/m}^2$ .
5. Subjects with known active hepatitis A, hepatitis B, or hepatitis C, with active or acute event of malaria, or who are known to be positive for human immunodeficiency virus (HIV).
6. Stroke requiring medical intervention  $\leq 24$  weeks prior to randomization.
7. Subjects taking direct acting oral anti-coagulants (DOACs) apixaban, dabigatran, rivaroxaban, edoxaban, or ticagrelor, or taking warfarin, are excluded due to the possibility of a cytochrome P450 (CYP)3A-mediated drug interaction, unless they stopped the treatment at least 28 days prior to randomization (Day 1); other oral anti-coagulants and anti-platelet drugs are permitted. Anti-coagulant therapies for prophylaxis of venous thromboembolism, including pulmonary emboli including when undergoing surgery or high-risk procedures, are allowed if low molecular weight heparins are used in the peri-operative period. Aspirin use ( $<100 \text{ mg per day}$ ) is allowed before and during the study.
8. Participated in another clinical study of an investigational agent (or medical device) within 30 days or 5 half-lives of date of informed consent, whichever is longer, or is currently participating in another study of an investigational agent (or medical device).
9. Platelet count  $>1000 \times 10^9/\text{L}$ .
10. For subjects on iron chelation therapy (ICT) at the time of ICF signing, initiation of ICT less than 24 weeks before the predicted randomization date. ICT can be initiated at any time during treatment and should be used according to the label.
11. Subjects who have had treatment with erythropoietin-stimulating agents  $\leq 24$  weeks prior to randomization.
12. Uncontrolled hypertension as defined by systolic BP  $\geq 160 \text{ mm Hg}$  or diastolic BP  $\geq 100 \text{ mm Hg}$ , medical intervention indicated, and more than one drug or more intensive therapy than previously used indicated.
13. Poorly controlled diabetes mellitus, in the opinion of the investigator, for example
  - 1) Hb A1c  $>9.0\%$  within 12 weeks prior to randomization (in the medical history);
  - 2) short-term hyperglycemia leading to hyperosmolar or ketoacidotic crisis; and/or
  - 3) history of diabetic cardiovascular complications.
14. Subjects who have major organ damage, including:
  - a. Liver disease with ALT or AST  $>3 \times \text{ULN}$ ; direct bilirubin  $>3 \times \text{ULN}$  with proportion of direct/total bilirubin  $>0.3$ ; or history/evidence of cirrhosis, liver transplant, or presence of clinically significant mass/tumor.
  - b. Heart disease, heart failure as classified by the New York Heart Association classification 3 or higher, or significant arrhythmia requiring treatment, or recent

myocardial infarction within 6 months of randomization, or significant cardiac iron overload.

- c. Severe lung disease, including pulmonary fibrosis or pulmonary hypertension, i.e.,  $\geq$ Grade 3 NCI CTCAE version 5.0.
- d. Significant kidney disease as indicated by, for example, estimated glomerular filtration rate  $<45$  mL/min/1.73 m^2 (per Modification of Diet in Renal Disease formula).

15. Subjects who have received chronic systemic glucocorticoids  $\leq$ 12 weeks prior to randomization ( $\geq$ 5 mg/day prednisone or equivalent). Physiologic replacement therapy for adrenal insufficiency is allowed.

16. Major surgery  $\leq$ 8 weeks prior to randomization.

17. A history of a clinically significant allergic reaction or hypersensitivity, as judged by the investigator, to any drug or any component of the study drug formulations used in the study (see Investigator's Brochure).

18. History or current malignancies (solid tumors and hematological malignancies) unless the subject has been free of the disease (including completion of any active or adjuvant treatment for prior malignancy) for  $\geq$ 5 years. However, subjects with the following history/concurrent conditions are allowed if, in the opinion of the investigator, the condition has been adequately diagnosed and is determined to be clinically in remission, and the subject's participation in the study would not represent a safety concern:

- a. Basal or squamous cell carcinoma of the skin
- b. Carcinoma in situ of the cervix
- c. Carcinoma in situ of the breast
- d. Incidental histologic finding of prostate cancer (T1a or T1b using the tumor, nodes, metastasis clinical staging system)

19. Screening or Baseline (Day 1) ECG demonstrating a QTcF  $>450$  ms in men and  $>470$  ms in women on 2 or more of the triplicate ECGs, or the presence of clinically significant ECG abnormalities as determined by the investigator.

20. Consumption/use of the following drugs or other substances within the specified time periods before randomization or plans to consume/use at any time during the study. If there is any question as to whether a substance is permitted, please review the product labelling (if applicable) and consult the medical monitor and/or sponsor.

- a. PDE type 5 inhibitors (including but not limited to sildenafil, tadalafil, and vardenafil) within 7 days prior to randomization (Day 1) or plans to use during the study.
- b. Grapefruit, grapefruit juice, grapefruit products, or herbal supplements with CYP-altering abilities within 1 week prior to randomization (Day 1) or plans to consume during the study.
- c. CYP3A-sensitive substrates, including the synthetic opioid fentanyl and alfentanil, or moderate to strong CYP3A inhibitors or inducers within 28 days prior to randomization (Day 1) or plans to use during the study.

- d. Any drugs or substances known to be substrates or inhibitors of P-gp or BCRP within 28 days prior to randomization (Day 1) or plans to use during the study.
- 21. Other prior or ongoing medical condition, physical findings, or laboratory abnormality that, in the investigator's opinion, could adversely affect the safety of the subject, make it unlikely that the course of treatment or follow-up would be completed, or impair the assessment of study results (e.g., a history of drug or alcohol abuse as judged by the investigator within the past 1 year).
- 22. Any clinically significant bacterial, fungal, parasitic, or viral infection requiring antibiotic therapy should delay screening/randomization (Day 1) until the course of antibiotic therapy has been completed. This includes but is not limited to long-term tuberculosis treatment.
- 23. Prior exposure to any of following:
  - a. IMR-687 or gene therapy
  - b. Sotatercept or luspatercept (Reblozyl®) within 6 months prior to randomization (Day 1)
- 24. In the opinion of the investigator, the subject is unable to meet the requirements of the study.

### **8.3. Screen Failures**

Any subject who consents to participate in the study but is not randomized will be considered a screen failure. Demographics, eligibility criteria, primary reason for screen failure, and any SAEs (if applicable) will be recorded and reported in the subject's electronic case report form (eCRF) for subjects who are screen failures.

If a subject is considered a screen failure, then he/she may be rescreened once with sponsor approval.

### **8.4. Guidelines for Withdrawal of Subjects from Study Participation**

Subjects will be informed that they can discontinue their participation in the study at any time and for any reason.

The investigator may also remove a subject from the study at their discretion if, in the investigator's opinion, it is not in the best interest of the subject to continue in the study.

If a subject must be discontinued from study participation, the medical monitor should be informed and consulted regarding possible appropriate assessments to be completed in advance of study discontinuation. In case of discontinuation from the study, every effort will be made to complete the early termination visit assessments, if possible. If a subject does not complete the early termination assessments, then every effort should be made to obtain end of study assessments. If a final visit is not feasible, every effort to collect follow-up medical records will be attempted.

In the case of subjects who are lost to follow-up, the study site must attempt to contact the subject by phone, making at least 3 documented attempts, each at least one week apart.

Additionally, one registered letter must have been sent with a copy on file. The study site should only deem the subject as lost to follow-up no less than 30 days following the first documented phone call attempt, unless circumstances preclude this (e.g., phone service has been discontinued or there is other evidence that contact is not feasible).

If the subject discontinues the study, the specific circumstances surrounding the discontinuation must be recorded in the subject's eCRF.

Refer to Section 7 for details about randomization and treatment assignments. All data collected prior to discontinuation must be recorded in the subject's eCRF.

Justifiable reasons to discontinue a subject from treatment (Section 8.5) and/or from the study may include, but are not limited to the following:

- The subject was erroneously included in the study (i.e., did not meet eligibility criteria)
- The subject experiences an SAE assessed as possibly or probably related to study drug
- The subject is unable to comply with the requirements of the protocol
- The subject participates in another investigational study
- The subject withdraws consent to participate in the study
- A subject for whom the blind is intentionally or accidentally broken

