**Duration of Treatment and Study Duration:**

The planned maximum duration of study participation is approximately 44 weeks. This consists of a screening period of up to 4 weeks, a treatment period of 36 weeks, and a 4-week safety follow-up assessment after the last dose of study drug is administered. In addition, there is retrospective data review undertaken at the start of subject participation that aims to collect information on transfusion activity during the 12 weeks preceding the Baseline (Day 1) visit (historical transfusion burden).

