## **8.5. Guidelines for Study Drug Dose Withholding or Discontinuation**

### **8.5.1. Safety Criteria for Study Dose Interruption or Discontinuation**

In consultation with the medical monitor, the investigator may decide to withhold the study drug or withdraw the subject in cases where tolerability or safety concerns emerge. Table 4 provides recommended guidelines for these decisions.

If a study drug dosing is withheld due to an AE (Section 12), subjects who continue on the study will have all assessments (except study drug administration) performed as per protocol.

If study drug dosing is discontinued for any reason, the specific circumstances surrounding the discontinuation must be recorded in the subject's eCRF. Any subject who discontinues study drug dosing must also be withdrawn from the study; however, all appropriate safety assessments and follow-up should be completed prior to withdrawal (Section 8.4).

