### 10.4. Emergency Unblinding

Unblinding is not always necessary to provide effective medical intervention and subject management in the event a subject experience an SAE, or an event that results in cessation of treatment (see Section 8.7). However, in the exceptional circumstance where the investigator believes that knowledge of the study drug assignment is essential to provide appropriate medical management, the treatment assignment for that subject will be provided to the investigator

according to standard operating procedures at the CRO. The medical monitor and sponsor are available to the investigator as needed for any considerations of unblinding a specific subject; however, the decision to unblind a specific subject relies solely on the clinical judgement of the investigator. That is, there is no requirement to discuss with the medical monitor and/or sponsor prior to unblinding a specific subject by the investigator; however, consultation is preferred. In the event that the investigator must unblind a subject and has not consulted with the medical monitor and/or sponsor, the investigator should notify the medical monitor and sponsor of the unblinding within 24 hours of breaking the blind.

After breaking the blind, the site staff should record the reason(s) for breaking the blind and any AEs leading to the breaking of the blind in the source documents and the appropriate eCRF pages. After breaking the blind, the subject will be discontinued from the study and should proceed with early termination and end of study visits as described in Section 8.4 and per the schedule of assessments ([Table 2](#) and [Table 3](#)).

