**Safety Reporting: Europe, Middle East, Asia-Pacific, and Africa**

**[contact]

**[contact]

Initial SAE reports must be followed by detailed descriptions. These should include copies of de-identified hospital case records and other documents when requested. If further information becomes available, the SAE Form should be updated with the new information and reported. The 24-hour notification requirement refers to reporting both initial SAE information and all follow-up SAE information once the site is made aware.

Serious adverse events occurring up to and including the subject's last study visit will be collected, regardless of the investigator's opinion of causation. A death occurring during the study and within 30 days after the last study visit must be reported to the sponsor or its designee with 24 hours of knowledge of the death regardless of causality. In addition, if the investigator learns of any SAE, including a death, at any time after a subject has been discharged from the study, and he/she considers the event to be reasonably related to the study drug or study participation, the investigator must promptly notify the sponsor.

For all SAEs the investigator must provide the following:

- Appropriate and requested follow-up information in the timeframe detailed above
- Causality of the SAE(s)
- Outcome of the SAE(s)
- Medical records and laboratory/diagnostic information

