10.1.4 Definition of Treatment-Emergence

A treatment-emergent adverse event (TEAE) is defined as an AE that starts after initiation of study drug, or an AE that existed pre-treatment and worsened in severity after initiation of study drug, through 30 days after the last dose of study drug.

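### The protocol contradicts itself on safety follow-up after early stopping of study drug, so a subject who completes the early termination visit can miss some or all of the planned 4-week post-dose observation

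*Protocol*

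**What the plan says.** Six places in the protocol bear on what happens after early stopping.

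- **Synopsis, Duration of Treatment and Study Duration.** "The planned maximum duration of study participation is approximately 44 weeks", made up of screening, 36 weeks of treatment and "a 4-week safety follow-up assessment after the last dose of study drug is administered".
- **Section 8.4.** The ET visit is sought where possible. The next sentence reads: "If a subject does not complete the early termination assessments, then every effort should be made to obtain end of study assessments". The medical monitor is to be consulted about assessments before the subject leaves.
- **Section 8.5.1.** "Any subject who discontinues study drug dosing must also be withdrawn from the study". A qualifier follows: "however, all appropriate safety assessments and follow-up should be completed prior to withdrawal (Section 8.4").
- **Section 10.4.** A subject whose blind is broken leaves the study and "should proceed with early termination and end of study visits". Section 8.4 and the schedules are cited as the place where these visits are described.
- **Tables 2 and 3, and 12.1.1.1.** End of Study is Week 40, Day 280 ±7, counted from Day 1. Adverse events (AEs) are recorded from consent to that visit. The ET visit repeats the Week 36 procedures without dosing or the trough PK sample.
- **Section 12.1.2.3.** "Serious adverse events occurring up to and including the subject's last study visit will be collected", whatever the judged cause. Beyond that point, deaths within 30 days of the last visit are reportable, as are SAEs the investigator learns of and considers reasonably related to study drug or participation.

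The SAP (10.1.4, and again in 13.6.2.1) classes an AE as treatment-emergent "through 30 days after the last dose of study drug".

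**The concern.** Safety and tolerability is the primary objective in both populations. A site that completes the ET visit has met the wording of 8.4 and may close the subject there, because 8.5.1 requires withdrawal and points to 8.4 for the follow-up owed first. SAE collection would then stop at that visit, apart from the two exceptions in 12.1.2.3.

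The subjects concerned include those with tolerability problems. Section 8.4 lists an SAE possibly or probably related to study drug as a reason to discontinue, and Table 4 directs withdrawal when certain drug-related events recur. If observation ends when they stop, events that start or worsen in the following weeks may never be recorded, although completers are watched for about four weeks. Effects after the last dose are not far-fetched on the protocol's own account: 5.2.3 says CYP3A induction is likely to take about a week to wash out.

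**Working it through.** **1. Reproduce the plan's own figure.** From the synopsis: 4 weeks of screening + 36 weeks of treatment + 4 weeks of follow-up = 44 weeks. This matches the stated maximum.

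**2. Post-dose observation scheduled for completers.** From Tables 2 and 3, the last dose is at Week 36 (Day 252 ±7) and End of Study is at Day 280 ±7.
- Nominal: 280 − 252 = 28 days.
- Shortest: (280 − 7) − (252 + 7) = 273 − 259 = 14 days.
- Longest: (280 + 7) − (252 − 7) = 287 − 245 = 42 days.

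**3. Post-dose observation for an early stopper closed at ET.** Observed time equals the gap from last dose to ET. The documents do not give this gap, so a range is assumed. Unobserved days = 28 − gap.

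| Assumed gap, last dose to ET (days) | Unobserved of the 28 scheduled days |
|---|---|
| 0 | 28 |
| 3 | 25 |
| 7 | 21 |
| 14 | 14 |

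**4. Does the tabulated End of Study visit fill the gap?** Not as written. Take a subject who stops on Day 84. Day 280 falls 280 − 84 = 196 days after the last dose, against the synopsis's 28. Neither table nor 12.1.1.1 says how the visit moves when dosing ends early.

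**5. Do the sections agree?**
- 8.5.1 asks for appropriate follow-up before withdrawal but names no visit, timing or length. It refers to 8.4.
- 8.4 supplies ET, with End of Study assessments only if ET is missed.
- 10.4 cites 8.4 as describing both visits. 8.4 does not ask for both.
- The synopsis times follow-up from the last dose; the schedules time it from Day 1.

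No passage clearly requires an End of Study visit 4 weeks after the last dose for early stoppers in general.

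**6. What is still captured after ET on the literal reading?** SAEs already reported are followed to resolution or stabilization (12.1.1.2). Deaths within 30 days of the last visit and related SAEs that come to the investigator's notice are reportable (12.1.2.3). New non-serious AEs, and new non-fatal SAEs not judged related, have no scheduled contact through which they would be collected.

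**The case against.** The best defence is that the protocol, read as a whole, intends follow-up. Section 8.4 does not say that End of Study is skipped once ET is done; its sentence can be read as a minimum for difficult cases. Section 8.5.1 puts safety follow-up before withdrawal. Section 10.4 shows that the authors took 8.4 to cover both visits. Section 12.1.1.1 records AEs to the End of Study visit with no exemption for early stoppers, and 12.1.1.2 obliges the investigator to follow reported events at later visits and calls. Section 14.3 even has sites seek permission to collect safety information at the end of the scheduled period from subjects who revoke consent.

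Much of this stands. A careful site may well do both visits, so the text allows follow-up to be lost but does not order it. The defence does not remove the conflict, however: the 8.5.1 safeguard leads back to the conditional rule in 8.4, and an intention to collect AEs to Week 40 does not create a contact for a withdrawn subject or give that contact a date.

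Three stronger inferences are tempting, and the documents do not support them.

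- *That the SAP's treatment-emergence rule presumes 30 days of observation.* It is a cut-off for classifying events. Completers are scheduled for only 28 days, 30 − 28 = 2 days short of it.
- *That under-recording differs by arm.* No discontinuation rates are given, by arm or overall.
- *That the lost follow-up can be totalled from the replacement allowance in 8.6 (up to 10 subjects per population).* That is a cap on replacements after dropout for any reason, not a forecast of how many will stop.

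**Conclusion.** The concern holds as an internal inconsistency with a practical consequence. Sections 8.4, 8.5.1 and 10.4 disagree on whether early stoppers have an End of Study visit in addition to ET. The synopsis and the schedules disagree on what that visit is timed from. On the literal reading of 8.4, a subject who completes ET can leave with 14 to 28 of the 28 scheduled post-dose days unobserved, for assumed gaps of 14 down to 0 days. The 28-day loss is the extreme case, with ET on the day of the last dose.

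A reader might conclude that early stoppers definitely lose their follow-up. The text supports only that they can, depending on how a site reads it. Because those stopping for toxicity are among them, post-dose AEs can be under-recorded for the primary objective. The effect on AE incidence, and any imbalance between arms, cannot be computed: the documents give neither the number of early stoppers nor the usual interval to ET.

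**What to change.** Reconcile 8.4, 8.5.1, 10.4, 12.1.1.1, 12.1.2.3 and Tables 2 and 3 with the synopsis.

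- **8.4:** say that subjects who stop study drug early are asked to complete the ET visit and also the End of Study safety follow-up, in place of seeking the latter only when ET is missed.
- **8.5.1:** name that follow-up as what should be completed before withdrawal takes effect. The withdrawal rule itself is not at issue here.
- **10.4:** its reference to 8.4 then becomes correct.
- **Tables 2 and 3:** time End of Study from the last dose, using the synopsis's own 4-week interval. For completers this leaves the nominal Day 280 unchanged, since 252 + 28 = 280.
- **12.1.1.1 and 12.1.2.3:** run AE and SAE collection through that visit for all treated subjects, instead of to a fixed Week 40 or an undefined last visit.

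The cost is protocol wording plus one already planned visit per discontinuing subject. Some will decline it, so the gap will narrow but not close entirely.

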## **8.5. Guidelines for Study Drug Dose Withholding or Discontinuation**

### **8.5.1. Safety Criteria for Study Dose Interruption or Discontinuation**

In consultation with the medical monitor, the investigator may decide to withhold the study drug or withdraw the subject in cases where tolerability or safety concerns emerge. Table 4 provides recommended guidelines for these decisions.

If a study drug dosing is withheld due to an AE (Section 12), subjects who continue on the study will have all assessments (except study drug administration) performed as per protocol.

If study drug dosing is discontinued for any reason, the specific circumstances surrounding the discontinuation must be recorded in the subject's eCRF. Any subject who discontinues study drug dosing must also be withdrawn from the study; however, all appropriate safety assessments and follow-up should be completed prior to withdrawal (Section 8.4).

